## 11. Potential Benefits

### Evidence of Direct Benefit to subjects

Benefit from metformin intervention: Our preliminary data shows that youth with T1D have IR, cardiac, vascular, muscle mitochondrial and exercise dysfunction. We also provide rationale that metformin may improve each of these abnormalities in the youth with T1D studied in this protocol, as well as likely improve BMI if overweight/obese, lipid profiles and glycemic control. Therefore T1D youth have clear evidence of likely benefit from being in the trial. In addition, all T1D youth, even if on placebo, will benefit from the screening tests for these complications that they are at increased risk for, and from the increased attention to checking blood sugars, the exercise prescription and from increased interaction with diabetes providers and educators.

There is potential benefit of participation by subjects with diabetes because the results of the Hb, HbA1C, and DEXA are made available to the patient/family and their health care provider. Because sedentary and obese adolescents are at increased risk for reduced bone mineral density, reduced exercise capacity, cardiovascular and muscle dysfunction and increased hepatic and visceral fat non-diabetic subjects may potentially benefit from the results of DEXA, cardiovascular, MRI and exercise testing. Subjects with diabetes have a condition which we will learn more about from performing this study.

The primary benefit from the clamp would be the discovery of undiagnosed insulin resistance. As mentioned before, surrogate measures are unable to detect IR adequately, and IR is the strongest predictor of CVD [12, 14, 187-189].. Discovery of IR would enable us to inform the family of an increased risk in the future for the individual for CVD, which may prompt them to seek greater screening tests when the individual is older. The direct benefit of

the isotopic tracers would be the differentiation of whether the liver, and/or the muscle and/or the adipose tissue are involved in the IR.

The echocardiogram can detect previously undiagnosed asymptomatic cardiac lesions such as mitral valve prolapse, bicuspid aortic valve, or small ASD/VSD in addition to any abnormal cardiac function. The blood tests done for screening can detect alterations in blood glucose, pubertal sex hormones, as well as abnormalities in fasting lipids. The risk of all of these endpoints is increased in T1D subjects, especially those who are also obese, and if left untreated can increase long term health risk, thus the benefit of detecting any of these would directly impact both the health and the longevity of the individual subject.

At the conclusion of the study, all subjects in the protocol will also be given counseling on the benefits of exercise as discussed above, and given an exercise prescription (as done as the standard of care in our pediatric metabolic syndrome clinic). The subjects will also be re-contacted once by phone call to follow-up on their study results and exercise recommendations. Sedentary subjects will thus also gain direct benefit from the study through the benefits of specialized counseling and recommendations for increased physical activity that would not otherwise be available to them.

### Evidence of Benefit to Society

The importance of the knowledge gained from this protocol is very high, since both T1D is a relatively common disease, increasing in prevalence in youth, and increases the risk of death from CVD and shortens lifespan. Diabetes mellitus is the third most prevalent severe chronic disease of childhood. Key research questions now focus on descriptive epidemiology (prevalence and incidence rates), etiology (metabolic, behavioral, genetic and immunologic risk factors), and appropriate treatment approaches. Macrovascular complications such as coronary artery disease continue to be the main cause of death in persons with diabetes, shortening average lifespan by 15 years, and were the topic of a recent NIH working group that evaluated opportunities to pathogenesis of and intervention to prevent CVD [10]. Although data to guide care of CVD in adults with diabetes are limited, even less data exist regarding the antecedents of CVD in youth with diabetes. Yet, these antecedents of adult CVD are present in children [190] with studies such as the Bogalusa Heart Study [191-193] and the Young Finns Study [194] demonstrating tracking of factors such as lipid levels and obesity. As CVD is the leading cause of death in people with diabetes and the antecedents develop in childhood, data to inform clinicians as to appropriate screening and treatment in this high-risk population are of great public health importance.

Our preliminary studies suggest that adolescents with T1D may already display symptoms of cardiovascular dysfunction including reduced exercise capacity, diastolic dysfunction, left ventricular hypertrophy and reduced vascular reactivity as measured by brachial artery ultrasound, endo-PAT plethysmography and Dynapulse. This has serious implications for the treatment of these patients as they age.

Traditional CVD risk factors remain important, but do not explain the excess risk of CVD in T1D [12]. Conventionally, T1D is considered a disease of insulin deficiency, leading to a research focus on improving insulin secretion or delivery to improve glucose control. However, a glucose-centric view may overlook the potential role of IR in T1D and CVD. Since IR is a contributor to accelerated atherosclerosis in the general population, superimposed IR may hasten the development of CVD in T1D [12, 14, 189]. In addition, due to rising rates of obesity in all youth, IR is likely to become increasingly important in the pathophysiology of T1D.

In addition, microalbuminuria and later diabetic kidney disease also likely contribute to increased risk of CVD. Preliminary evidence indicates that metalloproteinases (MMP) 2, 9, and 13 may be helpful noninvasive markers of kidney dysfunction. Elevated activity of these MMPs may be a biomarker specific for diabetic kidney disease in terms of glomerular basement membrane integrity. We hope that these tests may help to segregate out patients who will progress at a faster rate towards renal complications and therefore could be targeted for more intensive therapy.

Analysis of lipid subfractions with fast protein liquid chromatography (FPLC)[16] and apoB will help determine the baseline atherogenicity of lipid profiles in T1D youth, and the effects of improving IR on lipoprotein metabolism. Using apo B in combination with VLDL TG will allow interpretation of the effect of insulin on particle composition vs. particle number. By examining hepatic insulin sensitivity, and body composition proposed in Aim 2, and the vascular measures proposed, the relationship between lipid profiles and these factors can also be examined.

## **12. Alternative Treatment**

Insulin in T1D is the only alternative treatment and will still be continued.

### 13. Consideration of Specific Subject Categories

#### 1. Inclusion of Women

Every effort will be made to include approximately equal numbers of males and females in this protocol. The prevalence of T1D in adolescents is approximately equal in males and females, so we expect equal numbers of males and females being available for the study.

#### 2. Inclusion of Minorities

Every effort will be made to include a diverse subject distribution.

#### 3. Inclusion of Children

All subjects will be between ages 12 and 21. Insulin sensitivity needs to be studied in the adolescent age group as no data is currently available in this age group and it is critical to understand the pathophysiology of T1D in its developing stages.

## VI. Potential Scientific Problems

### Subject drop-out

To account for screen failures and potential 30% dropout, up to 100 subjects may be needed to be recruited to obtain the required 60 subjects. To limit drop-out, we maintain frequent contact with participants, use incentives for visits and adherence, and “surprise” incentives such as sports tickets and raffles to maintain contact with the study team. We find these strategies successful for maintaining compliance in our TODAY study participants. Due to our TODAY and other metformin studies, our staff is experienced with long-term adolescent studies, with excellent study retention for as long as six years. Adverse effects of metformin (nausea, anorexia, diarrhea and vomiting), have been shown to be minimized when the dose is titrated up slowly and taken with meals, and in our blinded study of metformin in obese adolescents, adverse effects did not result in decreased dose or significant patient attrition vs. placebo.

### Hypoglycemia during the insulin clamp

Hypoglycemia will be limited by monitoring blood sugars every five minutes, choosing a goal glucose well above the hypoglycemic range (95mg/dl), having IV access obtained prior to insulin administration, having two IVs in place in case problems arise with one IV, and leaving IV access in place until blood glucose values are stable after the study is completed. In addition, during the entire insulin infusion period, a pediatric CTSC nurse will remain at the bedside, and a Pediatric Endocrinologist (study Physician) or study Nurse Practitioner or study Physician Assistant will also remain at the bedside to minimize any risks associated with the insulin clamp.

### Inability to Stabilize Glucose Prior to Euglycemic Clamp

Stabilization of blood glucose by intravenous infusion of glucose and insulin should not be difficult in patients with reasonably well-controlled diabetes and is standard procedure. If serum glucose has not stabilized between 80-120 mg/dL by the start of the clamp, the clamp will be cancelled and the patient given the option to return for a second attempt within one week.

### Hepatic Glucose Output

Hepatic glucose output should be suppressed during the high dose clamp [195], but may not be in pubertal adolescents with higher Hba-1c [39], hence stable isotope tracer techniques will be used to measure hepatic glucose output.

### Variability in Subject Activity and Diet

Subject activity and diet that affect IR will be addressed by recruiting sedentary subjects, prescribing a standardized study diet (with carbohydrate content labeled for counting) and limiting strenuous exercise for 3 days prior to the clamp and exercise visits.

### Insufficient Number of Subjects

This is unlikely as the Barbara Davis Center for Childhood Diabetes is a very large, tertiary care center for type 1 diabetes, with approximately 3000 type 1 patients. Likewise, we have previous experience recruiting from these demographics for similar procedures.

### Hypoglycemia During Exercise Testing or Metformin Intervention

This will be limited by monitoring blood sugars before and after exercise and as needed, and having juice and snacks available in the exercise testing room as needed. In addition, subjects will be provided with a small meal following the VO2max test. Metformin may improve IR requiring insulin reductions, but with the expected mean A1c of 8.5% in our adolescent population, and an expected metformin effect of less than 1% change in A1c, significant hypoglycemia should not be common. Frequent blood sugar monitoring and contact with study staff will

help avoid hypoglycemia, and hypoglycemia was not significant in our preliminary studies or the metformin meta-analyses quoted. Metformin is well tolerated in youth and unlikely to present risk. On the contrary, it is likely to present benefit to the youth with T1D.

## **VII. Data Management and Security Plan**

### **Data Entry**

Data will be entered from paper forms. Once forms are completed, verified and corrected for inconsistencies, they will be manually entered at our site using a computerized data management system (Redcaps).

### **Edit Checks**

Computerized data validation routines will be used to enhance data quality and verify the accuracy of data within predefined value ranges. These checks include, but are not limited to: (a) initial screening of data, using logic and range checks built into data entry screens; (b) cross-form functional and consistency checks; and (c) edits assessing the serial integrity of data.

### **Disaster Recovery**

Routine data backup will occur on data in conjunction with the children's hospital secure server and Redcaps.

### **Security and Confidentiality**

All hard copy forms will be de-identified with a study number and filed in a locked cabinet, to which only the investigators will have access. Standard protection against computer hackers is implemented. Recovery from natural disasters (water, fire, or electrical) can occur through the ability to reconstruct both the database management system and the data from nightly backups.

## **VIII. Data and Safety Monitoring Plan**

The principal investigator and a Safety Officer, [name] will monitor the protocol and the safety of the research subjects. The PI will review all laboratory data and report any abnormal values to the patient and guardian and instruct the subject to follow-up with their PCP. The PI will report adverse events, and any decision to suspend or halt the protocol to the Safety Officer, CTRC and COMIRB immediately. She will meet every 6-12 months with the Safety Officer. She will also prepare a written report for the yearly continuing review required by the Safety Officer, COMIRB and the CTRC. There are no other entities that require notification about this protocol.

No protected health information will be collected until the appropriate HIPAA forms are completed. The protected health information that will be collected will include: Name and phone number, demographic information (age, sex, ethnicity, address, etc.), diagnosis (es), history and physical, laboratory or tissue studies, radiology studies, procedure results, survey/questionnaire results, research visit records, and portions of previous Medical Records that are relevant to this study. This information will be accessible only by the study investigators, Federal agencies overseeing human subject research, the Colorado Multiple Institutional Review Board, regulatory officials from the institution where the research is being conducted to monitor safety and compliance with policies.

### **A. Adverse Events (AE)**

The hyperinsulinemic euglycemic clamp is a standard procedure used in a large number of research studies and settings. Adverse events are uncommon when the procedure is done by experienced personnel in an appropriate setting.

#### **1. Adverse Event Definition**

For the purposes of this study, an Adverse Event (AE) is defined as any untoward medical event associated with the use of a drug in humans, whether or not considered drug-related. AEs also include any significantly abnormal physical finding identified on examination and any significantly abnormal laboratory result obtained on the patient between visits or at the time of the visit. Questions answered YES and any new abnormal physical findings are pursued by the study staff in order to determine the seriousness of the event and the need for further evaluation, follow-up, or referral.

##### **a) Adverse Event Reporting**

AEs are reported on a standard form that is completed by the study staff at each regular follow-up visit and phone interview. Adverse events reported or ascertained between clinic visits are captured and reported at the time of the next scheduled visit.

Pre-existing conditions (that is, conditions present prior to randomization) are not considered or recorded as AEs or SAEs unless the condition worsens in intensity or frequency after randomization. Likewise, continuing adverse events are not reported as AEs at subsequent visits unless they increase in severity or frequency between the visits, they result in criteria for an SAE, and/or they resolve between visits.

## **B. Serious Adverse Events (SAE)**

### **1. Serious Adverse Event Definition**

Events are divided into those that are not serious (AE) and those that are serious (SAE). The distinction between an SAE and an AE is a regulatory definition established by the FDA, not a clinical definition. The definition of SAE is not always related to clinical severity of the event. For the purposes of this study an AE is considered a Serious (SAE) when it satisfies any one of the following criteria:

- The event results in an inpatient hospitalization (any overnight stay associated with an admission).
- The event results in the prolongation of a hospital stay.
- The event results in permanent or severe disability.
- The event results in death.
- A pregnancy results in a congenital anomaly.
- The event results from an overdose (either accidental or experimental) of the study medication.
- The event is life-threatening.
- Treatment is required to prevent a serious event.
- The patient experiences a bout of lactic acidosis.
- An episode of severe hypoglycemia requiring assistance occurs.

There have been no SAE's in the research groups experience in the Pediatric CTRC. We do not anticipate encountering SAE's; however, we have identified the following as possible SAE's for the purposes of monitoring:

- Infection related to blood draw or IV placement
- Severe hypoglycemia during the euglycemic clamp or VO2 max test (blood glucose < 45 mg/dl)
- Severe adverse effects from taking placebo or metformin

### **a) Serious Adverse Event Reporting**

Study patients are instructed to contact the clinic with any serious adverse event meeting the above criteria. Each SAE is recorded on the study form and the PI is informed soon as possible after they occur and preferably within 24 hours of the notification of the clinic staff. This notification should occur even if data are incomplete. Additional data and follow-up information are documented and sent subsequently as an update to the original report. The PI immediately forwards SAE reports to the Safety Officer and COMIRB and any other required institutional monitoring committee.

## **C. Subject Discontinuation Criteria**

If a subject experiences any of the following, the subject will be withdrawn from the study.

1. Inability to complete study procedures
2. Inability of subjects to tolerate a minimum of 500 mg BID of metformin or placebo tablets
3. Development of anemia or renal dysfunction (anemia: hemoglobin < 9; renal dysfunction: creatinine >1.2)
4. Recurrent severe hypoglycemia (severe defined as symptomatic blood glucose < 45 mg/dl requiring assistance or seizure; recurrent as determined by PI)
5. Development of Lactic acidosis (as determined by PI)
6. Subject becomes pregnant during study

## **D. Protocol Stopping Criteria**

If one or more subjects experience any of the SAE's listed above, the PI will consult with the Safety Officer prior to continuing study visits with subjects. The Safety Officer and RSA will consult about the significance of the SAE's and make a recommendation to the PI.

# **VIII. Data Analysis Plan**

## **A. Data Analysis Plan**

Data analyses and power: For all aims, variables will be checked for the distributional assumption of normality and appropriate transformations applied to normalize the data.

Specific Aim 1a: A placebo-controlled design will be employed using a mixed effect model to determine the effect of treatment and check for the effect of sequence on the effects of metformin to placebo on whole body IR (GIR, mg/kg/min, 1o outcome). Based on the Sarnblad et al article, who had a mean difference of 0.8 and SD of 0.9, with a sample size of 30 per group and an alpha of 0.05, we will have 92% power to detect a difference of 0.8 in the primary outcome of insulin sensitivity. Additional 10 patients will be recruited per/group for a total N = 80 to account for 30% dropout. 100 will be screened to account for screen failures.

Specific Aim 1b: A placebo-controlled design will be employed using a mixed effect model to determine the effect of treatment on the effects of metformin to placebo on ADP t $\frac{1}{2}$  adjusting for baseline mitochondrial function, gender, and Tanner stage. Our preliminary baseline data shows a difference in ADP t $\frac{1}{2}$  between T1D and controls (19.1  $\pm$  0.85 vs. 14.6  $\pm$  0.63, respectively), or an effect size = 5.294. Assuming that T1D patients treated with metformin improve ADP t $\frac{1}{2}$  compared with placebo, we will have > 80% power to detect an effect size as small as 0.645 and a two-sided  $\alpha$  = 0.0125 adjusted for 4 endpoints.

Specific Aim 2a: A placebo-controlled design will be employed using a mixed effect model to determine the effect of treatment on the effects of metformin to placebo on BrachD, adjusting for baseline BrachD, gender, and Tanner stage. Agarwal *et al* demonstrated a mean difference between 3 months of metformin and placebo in young women with PCOS using Aix (-6.1; 95% CI of -8.46-3.74)[93]. If we see a similar effect with common SD = 5.066 calculated from the CI, N = 11 per/group is required for 80% with a two-sided  $\alpha$  = 0.0125 to adjust for 4 endpoints, thus with N = 80 we will have > 99% power for this aim.

Specific Aim 2b: A mixed effect model will be used to compare the effects of metformin to placebo on cardiac dysfunction measured by CS. With N = 80 we will have > 80% power to detect an effect size as small as 0.645 and a two-sided  $\alpha$  = 0.0125 adjusted for 4 endpoints.

Secondary Analysis: For all Aims, correlations will also be made between each primary outcome and IR, A1c, T1D duration, and BMI as continuous measures with Pearson correlation coefficients without adjustment for covariates. Multivariate linear regression will determine which outcomes relate independently to IR, A1c, T1D duration, BMI and/or gender after adjusting for covariates. Similar analyses will assess for correlations between changes in IR, A1c and BMI on changes in each primary outcome to the intervention.

Exploratory analyses: Secondary outcomes will be analyzed at baseline and correlations between potential contributors to each outcome will be examined with Pearson or Spearman correlation coefficients, as appropriate. Multivariate linear regression will then determine which potential contributors independently relate to each baseline measure, adjusting for covariates. A mixed effect model will also be used to compare the effects of metformin to placebo on exploratory outcomes.

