### **2. Enrollment**

The recruitment goal is to screen 100 T1D subjects to obtain 60 completers. This number was determined on the basis of power calculations and the number of available subjects likely to participate.

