After an initial screening visit (Table 2 above, Visit 1), 100 T1D adolescents will be asked to come in for initial measurements to obtain baseline measurements. . All participants will undergo the following assessments prior to randomization: a, muscle/aortic MRS assessment (Visit 2, MRS 1) and a cardiovascular and VO2peak assessment (Visit 3, CV 1 ) and hyperinsulinemic euglycemic clamp and Dexa Scan (Visit 4, Clamp 1). After completion of the baseline assessment visits, subjects will then be randomized to 3 months of double-blinded metformin or placebo,. They will have an interim brief visit (Visit 5) to assess blood sugars, insulin dose, compliance and side effects. A phone call will also be done twice in between the baseline and pill count visit and between the pill count and final outcomes visits. At completion of the treatment phase, all participants will undergo repeat outcomes assessments (identical to baseline assessments): a muscle/aortic MRS assessment (Visit 6, MRS 2), a cardiovascular and VO2peak assessment (Visit 7, CV 2 ), and a hyperinsulinemic euglycemic clamp and Dexa Scan (Visit 8, Clamp 2). The treated and untreated Assessments will then be compared to determine the impact of metformin vs. placebo on the outcomes.

**Intervention:** T1D subjects will be randomized by our CTRC pharmacist in a double-blinded fashion at the end of Visit 4 to either active metformin or identical-appearing placebo. Randomization is stratified by: 1) HbA1c above or below 8.5% (mean HbA1c in our preliminary studies) 2) BMI above or below the 85th percentile. The metformin and placebo randomization and dispensing will be done as in our ongoing obesity study (PI [name], COMIRB# 07-0988).

Each participant is provided with a pill dispenser, a calendar to record doses, a study glucose meter and strips, and a log sheet to record glucose levels and insulin dose changes. Participants are asked to check their blood sugar ≥4 times a day, check urine ketones if blood sugar is >than 300mg/dl for more than two readings, and contact the study staff if they have large urine ketones, 2 or more blood sugars <65 mg/dl in any week or any hypoglycemia requiring assistance, any of which will trigger blood sugar adjustment. Subjects will otherwise adjust their insulin as routinely recommended at our center, and are asked not to make changes to the type or

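### N = 80 covers 25% dropout, not the stated 30%: at 30% it leaves 56 completers, 4 short of the planned 60 (minor arithmetic error; small effect on Aim 1a power)

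*Combined protocol and SAP*

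**What the plan says.** Three places in the combined protocol and SAP bear on the size of the trial.

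- **Data Analysis Plan, Specific Aim 1a.** The inputs come from a cited metformin trial, "who had a mean difference of 0.8 and SD of 0.9, with a sample size of 30 per group and an alpha of 0.05", and the result is that "we will have 92% power to detect a difference of 0.8 in the primary outcome of insulin sensitivity". The allowance for losses follows: "Additional 10 patients will be recruited per/group for a total N = 80 to account for 30% dropout". One hundred are to be screened to cover screen failures.
- **Section IV.2, Enrollment.** "The recruitment goal is to screen 100 T1D subjects to obtain 60 completers". The section says this number rests on the power calculations and on how many patients are available.
- **Section VI, Subject drop-out.** Allowing for screen failures and a possible 30% dropout together, "up to 100 subjects may be needed to be recruited to obtain the required 60 subjects".

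The plan therefore commits to three figures: 80 randomised, 30% dropout and 60 completers.

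**The concern.** To finish with a given number after losing a fraction d, the starting number is the target divided by (1 − d). Adding 10 to 30 is an increase of one third, and an increase of one third offsets a loss of one quarter. The plan labels it as an allowance for 30%.

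What is at stake is whether the trial, run as planned and losing patients at the rate the plan itself expects, reaches the number of completers that it calls required and on which it bases the power for its first primary outcome.

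**Working it through.** **Inputs.** All are from the Data Analysis Plan, Specific Aim 1a, unless noted.

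- Difference in GIR 0.8, SD 0.9, so the standardised difference is 0.8 / 0.9 = 0.889.
- 30 evaluable per group; alpha 0.05; stated power 92%.
- 10 added per group, N = 80, dropout 30%, 100 screened.
- Target of 60 completers (Enrollment; Subject drop-out).
- Assumptions: Aim 1a is tested two-sided (not stated for this aim), and dropout is equal in the two groups.

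**Step 1: reproduce the stated power.** For a two-sample t-test with n per group, the noncentrality is 0.889 × √(n/2), with 2n − 2 degrees of freedom.

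- n = 30: 0.889 × √15 = 3.44, 58 df, power 92.3%.
- The normal approximation gives 93.1%. A one-sided t-test would give 96.1%.

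The stated 92% reproduces as a two-sided test with 30 per group, so the power calculation itself is sound.

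**Step 2: completers from N = 80.**

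- 80 × (1 − 0.30) = 56, or 40 × 0.70 = 28 per group.
- Shortfall against 60: 60 − 56 = 4.

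**Step 3: the dropout that N = 80 does cover.**

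- 1 − 60/80 = 0.25, that is 25%.

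**Step 4: the number that 30% dropout would need.**

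- 60 / 0.70 = 85.7, rounded up to 86 (43 per group).
- Multiplying instead of dividing gives 60 × 1.3 = 78 (39 per group), close to 80. That may be how the figure arose, but the plan does not show its derivation.

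**Step 5: effect on Aim 1a.**

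| Per group | Completers | Power, t-test | Power, normal approximation |
|---|---|---|---|
| 30 | 60 | 92.3% | 93.1% |
| 28 | 56 | 90.4% | 91.4% |

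The loss is 92.3 − 90.4 = 1.9 percentage points by t-test. The difference detectable with 92% power moves from about 0.80 to about 0.82. By the same t-test, 80% power for a difference of 0.8 needs 21 per group.

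**The case against.** **The 100 in the Subject drop-out section might absorb the gap.** It does not. That 100 covers screen failures as well as dropout, and the Data Analysis Plan uses the same 100 as the number screened, with 80 recruited. Going from 100 to 80 implies 20% screen failure; obtaining 86 from 100 would require 14% or less.

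**The primary analysis keeps everyone randomised.** The Analysis plan specifies intent-to-treat with multiple imputation of missing GIR, so 60 is a planning figure and not the analysis set. That is correct, but imputing a missing outcome adds little information. The plan also repeats the analysis without imputation, which at 30% dropout would use about 56 patients. The arithmetic point stands.

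**The planned ANCOVA may be more efficient than the t-test used here.** This also has force. If the SD of 0.9 is not already adjusted for covariates, which the documents do not say, a correlation of 0.3 between covariates and outcome would reduce it to 0.9 × √(1 − 0.09) = 0.859 and bring power at 28 per group to 92.8%. The uncertainty in the power is thus at least as large as the loss shown above.

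**Thirty per cent is only an allowance.** The Subject drop-out section calls it potential, and the Enrollment section calls 60 a goal. This makes the error minor; it does not make the figures agree.

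**Stronger readings that the documents do not support.** A reader might infer that the promised 92% power is lost and Aim 1a is underpowered. The plan ties 92% to 30 per group, where it reproduces, and does not set it as a minimum under 30% dropout. A reader might also take the Study Visits narrative, "100 T1D adolescents will be asked to come in for initial measurements to obtain baseline measurements", as a further contradiction with 100 screened. That sentence is loosely worded, but the description of Visit 1 invites only those who meet the entry criteria to the baseline assessments, and the sentence has no bearing on the dropout calculation.

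**Conclusion.** The sample-size statement for Aim 1a is wrong as written, and the error is minor. N = 80 allows for 25% dropout; at the stated 30% it is 6 short of the 86 needed and misses the target by 4 completers. No other section repairs this.

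Aim 1a remains adequately powered, at about 90% for a difference of 0.8. The completer counts rest only on the plan's own figures. The power figures also assume a two-sided 0.05, equal dropout in the groups, an unadjusted comparison, and an SD of 0.9 that carries over to this trial.

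**What to change.** Make the Enrollment section, the Subject drop-out section and the Specific Aim 1a paragraph agree, in one of two ways:

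1. **Keep 60 completers and 92% power, and change the rate.** State that 80 randomised yields 60 completers (30 per group) if dropout is at most 25%. This is open only if the sponsor can support 25%.
2. **Keep 30% dropout, and change the yield.** State that 80 randomised is expected to give 56 completers (28 per group) and about 90% power for a difference of 0.8 in Aim 1a, and replace 60 with 56 as the expected number in the other two sections.

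Either is a change of wording with no extra patients. The first requires a justification for the lower rate; the second lowers the quoted power by about 2 points and the completer figure by 4. Raising N to 86 would also reconcile the figures, but it means 6 more patients, and the small power loss in Aim 1a does not call for that.
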